3.2.1 Formulation

Atezolizumab injection for intravenous use is a sterile, preservative-free, colorless to slightly yellow solution in single-dose vials. Each 20 mL vial contains 1200 mg of atezolizumab and is formulated in glacial acetic acid (16.5 mg), L-histidine (62 mg), polysorbate 20 (8 mg), and sucrose (821.6 mg), with a pH of 5.8.

3.2.2 Storage

Atezolizumab injection is a sterile, preservative-free, and colorless to slightly yellow solution for intravenous infusion supplied as a carton containing one 1,200 mg/20 mL single-dose vial (NDC 50242-917-01).

Store vials under refrigeration at 2°C to 8°C (36°F to 46°F) in original carton to protect from light. Do not freeze. Do not shake.

3.2.3 Dispensing

3.2.3.1 Preparation

Visually inspect drug product for particulate matter and discoloration prior to administration, whenever solution and container permit. Discard the vial if the solution is cloudy, discolored, or visible particles are observed. Do not shake the vial. Prepare the solution for infusion as follows. Withdraw the required volume of atezolizumab from the vial(s) using sterile needle and syringe. Dilute to a final concentration between 3.2 mg/mL and 16.8 mg/mL in a polyvinyl chloride (PVC), polyethylene (PE), or polyolefin (PO) infusion bag containing 0.9% Sodium Chloride Injection, USP. Dilute with only 0.9% Sodium Chloride Injection, USP. Mix diluted solution by gentle inversion. Do not shake. Discard used or empty vials of atezolizumab.

3.2.3.2 Storage of Infusion Solution

This product does not contain a preservative. Administer immediately once prepared. If diluted atezolizumab infusion solution is not used immediately, store solution either:

1. At room temperature for no more than 6 hours from the time of preparation. This includes room temperature storage of the infusion in the infusion bag and time for administration of the infusion, or
2. Under refrigeration at 2°C to 8°C (36°F to 46°F) for no more than 24 hours from time of preparation.

Do not freeze. Do not shake.

3.2.4 Dosage

Administer atezolizumab as 1200 mg every 3 weeks.

3.2.5 Administration

Please see the manufacturer's package insert for administration instructions.

3.2.6 Missed Doses

Patients who do not receive an intended atezolizumab infusion should have the infusion administered as soon as possible. If an intended infusion is delayed by more than 48 hours, the Principal Investigator should be consulted to guide dosing re-start. Patients who miss an extended number of bomedemstat doses or exhibit serial non-compliance with treatment may be removed from the study at the discretion of the Principal Investigator.

3.2.7 Dose Modifications for Toxicity

Please see the manufacturer's package insert for detailed information regarding dosage modification for toxicities of atezolizumab.

4.0 STAGING CRITERIA

Limited stage (LS) and extensive stage (ES) disease are defined as follows:

1. Limited stage disease: Tumor and any metastases to regional lymph nodes (hilar, mediastinal, or ipsilateral supraclavicular) are confined to one hemithorax and can be encompassed in a single radiation port.
2. Extensive stage disease: Extension of disease beyond the areas defined for limited disease.

Note: A cytologically confirmed malignant pleural effusion constitutes extensive stage disease. Patients who have progressed following treatment for limited stage small cell lung cancer are considered to have extensive stage disease.

See Section 15.1 for VALG staging details.

5.0 ELIGIBILITY CRITERIA

Subjects must meet all the enrollment criteria to be eligible for this study. Eligibility criteria may not be waived by the investigator.

5.1 Inclusion Criteria

Patients must meet all of the following applicable criteria to be eligible for enrollment:

1. Adult aged 18 years or older and willing and able to provide written informed consent.
2. Histologically confirmed diagnosis of extensive stage small-cell lung cancer (ES-SCLC).

Note: Previously treated limited stage SCLC (LS-SCLC) patients are eligible if disease progression had occurred following completion of definitive treatment for LS-SCLC. Determination of disease progression after prior therapy for LS-SCLC is at the discretion of the investigator.

3. Having received four cycles of platinum-etoposide concurrent with three or four cycles of immune checkpoint inhibitor as induction systemic therapy for ES-SCLC immediately prior to study enrollment (see below for definitions). Note that immune checkpoint inhibitor may have been omitted from the first cycle only.

Platinum is defined as cisplatin or carboplatin. Immune checkpoint inhibitor is defined as atezolizumab, durvalumab, or other anti-PDL1 or anti-PD1 monoclonal antibody that is approved by the US Food and Drug Administration for first-line treatment of ES-SCLC in combination with platinum and etoposide at the time of treatment receipt. Immediately prior is defined as receipt of Cycle 1 Day 1 of platinum-etoposide +/- immune checkpoint inhibitor no more than 112 days prior to Cycle 1 Day 1 of study treatment, and administration of fourth cycle of platinum-etoposide and immune checkpoint inhibitor no more than 30 days prior to Cycle 1 Day 1 of study treatment.

4. Eligible to receive maintenance atezolizumab, as defined by stable disease or better, following induction platinum-etoposide and immune checkpoint inhibitor. Determination of response to induction therapy is at the discretion of the investigator. Investigators should contact the PI if clarification is needed.
5. ECOG performance status of ≤ 2 .
6. Minimum life expectancy of ≥ 12 weeks.
7. Satisfactory laboratory parameters:

- a. Absolute neutrophil count (ANC) $\geq 1000/\text{mcL}$

Note: myeloid growth factor use within 14 days of study treatment initiation is not permitted. Growth factor may have been previously administered during induction chemoimmunotherapy.

- b. Platelet count (Plt) $\geq 75 \times 10^3/\text{mcL}$ (without transfusion)
- c. Hemoglobin (Hgb) $\geq 8.0 \text{ g/dL}$ (transfusion is permitted)
- d. Calculated glomerular filtration rate (GFR; using the Cockcroft-Gault equation) $\geq 40 \text{ mL/min}$ or serum creatinine $\leq 1.5 \times$ upper limit of normal
- e. Serum total bilirubin $\leq 1.5 \times$ upper limit of normal (ULN) or $\leq 3 \times$ ULN for subjects with Gilbert's disease
- f. Serum alanine aminotransferase (ALT) and aspartate aminotransferase (AST) $\leq 2.5 \times$ ULN ($\leq 5 \times$ ULN if evidence of hepatic involvement by malignant disease)

g. The following coagulation parameters must be met only in patients not receiving anticoagulant agents at baseline.

- i. international normalized ratio (INR) < 1.5x upper limit of normal
- ii. activated partial thromboplastin time (aPTT) < 1.5x the local upper limit of normal

Note: there is no INR or aPTT threshold for patients who are receiving anticoagulant agents at baseline, but patients must be on a stable dose of anticoagulant, and discontinuation of all anticoagulation while the platelet count is below $50 \times 10^3/\text{mL}$ must be deemed appropriate for the patient by the investigator prior to enrollment (see Section 5.2).

8. Able to swallow capsules.
9. Amenable to peripheral blood sampling during the study.
10. Female subjects of childbearing potential should be willing to use 2 methods of birth control or abstain from heterosexual activity for the course of the study through 28 days after the last dose of study medication. Subjects of childbearing potential are those who have not been surgically sterilized or have not been free from menses for >1 year.
11. Male subjects who are sexually active with female partner(s) of childbearing potential should be willing to use an adequate method of contraception starting with the first dose of study therapy through 28 days after the last dose of study therapy.

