6.0 TREATMENT PLAN

6.1 Study Overview

This is an open label, single arm, single institution Phase 1-2 study testing the activity and tolerability of the LSD1 inhibitor bomedemstat in combination with maintenance immune checkpoint inhibitor (ICI) in patients with newly diagnosed extensive stage SCLC treated with first-line induction platinum-etoposide and ICI. Bomedemstat dosing will be titrated to platelet count suppression (an on-target toxicity). Consideration of bomedemstat dose escalation will occur on an every three week schedule. As such, for convenience, all patients will receive the ICI atezolizumab in combination with bomedemstat, including patients who received a different ICI as part of induction with platinum-etoposide.

The starting dose of bomedemstat will be determined according to the screening platelet count as follows. For patients with a platelet count of $\geq 100 \times 10^3/\text{mCL}$, the starting dose will be 0.5 mg/kg/d. For patients with a platelet count of $75-99 \times 10^3/\text{mCL}$, the starting dose will be 0.4 mg/kg/d. See Sections 2.7 and 3.1.4 for bomedemstat starting dose selection rationale. A safety evaluation will be performed as described in Section 10.2 and the starting dose will be modified accordingly, if necessary.

Bomedemstat will be administered orally, once daily, for a 21-day cycle. Bomedemstat should be taken on an empty stomach. See Section 3.1.5 for detailed administration instructions. Because bomedemstat exhibits on-target toxicity of lineage-specific myelosuppression that preferentially affects platelet production, bomedemstat dosing will be titrated to a target platelet count of $50-99 \times 10^3/\text{mCL}$ as described in Section 6.2. Detailed guidance regarding bomedemstat dose modification for toxicities (including myelosuppression) is described in Section 6.3.

Atezolizumab will be administered via IV infusion at a flat dose of 1,200 mg every 3 weeks in keeping with the medication's prescribing information regarding standard of care use⁴⁶.

Subjects who at any time experience severe toxicity meeting criteria for treatment discontinuation (see Section 6.6.2) will not be eligible for further study treatment and will be converted to Off Treatment status.

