8.6.3.2 Paternal exposure

Male patients should refrain from fathering a child or donating sperm during the study and for 30 days after the last dose of bomedemstat and 90 days after the last dose of atezolizumab, whichever is longer.

Pregnancy of the patient's partner is not considered to be an AE. However, the outcome of all pregnancies (spontaneous miscarriage, elective termination, ectopic pregnancy, normal birth, or congenital abnormality) occurring from the date of the first dose until 90 days after the last dose of study treatment, if possible, be followed up and documented.

Where a report of pregnancy is received, prior to obtaining information about the pregnancy, the Investigator must obtain the consent of the patient's partner. Therefore, the local study team should adopt the generic ICF template in line with local procedures and submit it to the relevant Ethics Committees (ECs)/Institutional Review Boards (IRBs) prior to use.

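### Inclusion criterion 11 asks men to commit to contraception for 28 days after the last dose, 2 to 62 days less than section 8.6.3.2 requires of them

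*Combined protocol and SAP*

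**What the plan says.** Two places in the protocol set a post-treatment period for men.

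- Section 5.1, criterion 11, covers men who are sexually active with female partners of childbearing potential. They should be willing to use adequate contraception "starting with the first dose of study therapy through 28 days after the last dose of study therapy".
- Section 8.6.3.2 opens with "Male patients should refrain from fathering a child or donating sperm during the study" and extends this "for 30 days after the last dose of bomedemstat and 90 days after the last dose of atezolizumab, whichever is longer". It also asks that partner pregnancies be followed, where possible, up to 90 days after the last study treatment.

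Three other statements bear on how these fit together. Section 5.0 says "Eligibility criteria may not be waived by the investigator". Section 6.1 says "all patients will receive the ICI atezolizumab in combination with bomedemstat", whichever checkpoint inhibitor was used in induction. The schedules are "Administer atezolizumab as 1200 mg every 3 weeks" (section 3.2.4) and "Bomedemstat will be administered orally, once daily, for a 21-day cycle" (section 6.1).

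Nothing in the document explains why the two periods differ or says which one governs.

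**The concern.** Criterion 11 is where a man's willingness to prevent conception is tested before he enters. Its 28 days is shorter than both limbs of section 8.6.3.2, including the 30-day limb for bomedemstat alone. A man who would accept 28 days but not 90 meets the criterion as written, and once treated he falls under a rule to which he was never asked to agree.

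The follow-up schedule is not built to catch this. The Safety Follow-Up Visit is about 30 days after treatment stops (section 8.5.3.2), by which time the 28-day commitment has lapsed. Men who stop for progression then move to survival checks every 12 weeks, which may be done from medical records (section 8.5.3.4). Men who stop for other reasons do have monitoring visits every 8 weeks (section 8.5.3.3).

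What is at stake is reproductive safety and what participants are asked to accept. No statistical property of the trial depends on it.

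**Working it through.** The plan gives no figure of its own to reproduce, so the check is date arithmetic.

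**Inputs**

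- Criterion 11: 28 days after the last dose of study therapy (section 5.1).
- Conduct rule: 30 days after bomedemstat and 90 days after atezolizumab, whichever is longer (section 8.6.3.2).
- Atezolizumab every 3 weeks (section 3.2.4); bomedemstat daily in 21-day cycles (section 6.1).

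**Readings used.** The last dose of study therapy is the later of the two drugs' last doses. The conduct rule ends on the later of its two calendar dates.

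**Formulas.** Let A be the day of the last atezolizumab infusion, B the day of the last bomedemstat dose, and d = B − A.

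- Criterion 11 ends on day max(A, B) + 28.
- Section 8.6.3.2 ends on day max(B + 30, A + 90).
- Shortfall = max(B + 30, A + 90) − max(A, B) − 28.

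Set A = 0. If d ≤ 0, the shortfall is 90 − 28 = 62. If d > 0, it is max(d + 30, 90) − (d + 28), which equals max(2, 62 − d).

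| Stopping order | Criterion 11 ends (day) | 8.6.3.2 ends (day) | Shortfall (days) |
|---|---|---|---|
| Atezolizumab last, or same day (counted from the last infusion) | 28 | 90 | 62 |
| Bomedemstat 20 days later | 48 | 90 | 42 |
| Bomedemstat 21 days later | 49 | 90 | 41 |
| Bomedemstat 42 days later | 70 | 90 | 20 |
| Bomedemstat 60 days later | 88 | 90 | 2 |
| Bomedemstat 120 days later | 148 | 150 | 2 |

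Evaluating the formula for every d from −400 to +400 days gives a minimum of 2 and a maximum of 62. It never reaches zero.

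**Ordinary case.** If both drugs run on schedule and stop within the same cycle, d lies between 0 and 20 and the shortfall is 42 to 62 days. The 2-day end requires at least 60 days of bomedemstat after the last infusion. Section 6.3 lets atezolizumab be discontinued for toxicity under its prescribing information, so such a lag is conceivable, but no section expressly provides for prolonged bomedemstat alone.

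**After alignment.** If criterion 11 ends on day max(B + 30, A + 90), the shortfall is 0 for every d.

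**The case against.** The strongest reply is that the men are already protected. The two rules are nested: a man who follows 8.6.3.2 also satisfies criterion 11, and criterion 11 does not say that restrictions end on day 28. This is correct, and it limits the point to the entry commitment. It does not remove the mismatch, because the entry test still admits a man who is unwilling to meet the later rule.

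The partner-pregnancy follow-up in 8.6.3.2 runs to 90 days after the last study treatment. Counted from the later drug, that is day max(A, B) + 90, which is never earlier than the end of the conduct rule, so it spans every shortfall day. That also stands, but it records pregnancies and does not prevent them.

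The consent form is not available, so it is not known what participants are told. If the form already gives the longer period, the practical harm is small and the conflict with criterion 11 remains.

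The documents do not show pharmacologically which period is right; that would need outside sources. They show only that the protocol's section on paternal exposure sets 30 and 90 days by drug and uses 90 days again for pregnancy follow-up. Taking the longer period is the cautious choice and leaves the more specific rule intact.

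Finally, 8.6.3.2 also restricts men during the study, and it does not say whether that includes survival follow-up. If it does, the restriction lasts longer and the difference is no longer the 2 to 62 days computed here. That makes the size less certain but does not bring the two rules into agreement.

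**Conclusion.** The concern holds. Criterion 11 commits men to a shorter period than the protocol later imposes on the same men, and nothing reconciles the two. The shortfall is 2 to 62 days, and 42 to 62 days when both drugs stop on schedule within one cycle.

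These figures rest on the two readings stated in the working and on taking the study, in 8.6.3.2, to end for this purpose with treatment. Contraception and not fathering a child are treated as comparable because both control the risk of conception after dosing. The number of men affected cannot be estimated from the documents.

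This is an inconsistency on a participant-safety point and should be corrected. It does not touch the sample size, power, dose-limiting toxicity rule, stopping rules or analysis.

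**What to change.** In criterion 11, replace the 28-day end point with the period in section 8.6.3.2: 30 days from the final bomedemstat dose or 90 days from the final atezolizumab dose, whichever date falls later. Leave the period in 8.6.3.2 unchanged, and confirm that the consent form states the same one.

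The cost is a one-line protocol amendment and a check of the consent form. Visits, data collection and analysis do not change.

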5.2 Exclusion Criteria

Subjects meeting any of the following exclusion criteria are not eligible for study participation:

1. Prior receipt of systemic therapy for ES-SCLC other than four cycles of induction platinum- etoposide and immune checkpoint inhibitor (see Section 5.1 for definitions of these terms).
2. Diagnosis of LS-SCLC that has not been previously treated.
3. Receipt of radiation therapy for symptomatic deterioration and/or radiographic disease progression that was administered after initiation of induction platinum- etoposide and immune checkpoint inhibitor.

Note: the presence of untreated asymptomatic brain metastasis, or a history of receipt of radiation to brain metastasis that was not initiated in response to symptomatic deterioration and/or radiographic disease progression following initiation of induction systemic therapy, does not preclude study participation. Investigators should contact the PI if clarification is needed.

4. Anticipated use of prophylactic cranial irradiation or consolidative thoracic radiation therapy during study participation.

Note: Palliative radiation to the CNS for new CNS disease that develops during study participation is allowed (Section 8.2.7.1).

5. History of prior immune-related adverse event or other toxicity associated with immune checkpoint inhibitor that precludes safe administration of maintenance atezolizumab, in the opinion of the investigator.

6. Current or prior use of immunosuppressive medication within 14 days prior to the first dose of study treatment. The following are exceptions to this criterion:
 - a. Intranasal, inhaled, topical steroids or local steroid injections (e.g., intra-articular injection).
 - b. Systemic corticosteroids at doses not to exceed 10 mg/d of prednisone or equivalent.
 - c. Steroids as premedication for hypersensitivity reactions (e.g., CT scan premedication).
7. Active autoimmune disease requiring systemic immunosuppression or history of autoimmune disease requiring systemic immunosuppression within the last 2 years.

Note: Systemic immunosuppression should be interpreted as systemic glucocorticoids at a dose of greater than 10 mg/day of prednisone or equivalent, systemic biologic agents including monoclonal antibodies against inflammatory mediators, or small molecule agents. Investigators should contact the PI if clarification is needed.

8. Active pneumonitis or interstitial lung disease (ILD), or a history of pneumonitis/ILD, which required systemic immunosuppression (e.g. corticosteroids).
9. Known bleeding disorder (e.g., dysfibrinogenaemia, factor IX deficiency, hemophilia, Von Willebrand's disease, Disseminated Intravascular Coagulation [DIC], fibrinogen deficiency, or other clotting factor deficiency), at the discretion of the investigator.
10. History of severe thrombocytopenia or platelet dysfunction, including: immune thrombocytopenic purpura; thrombotic microangiopathy including thrombotic thrombocytopenic purpura, hemolytic-uremic syndrome, complement-mediated thrombotic microangiopathy, or drug-induced thrombotic microangiopathy; inherited platelet function disorders, including Bernard-Soulier Syndrome, gray platelet syndrome, Wiskott-Aldrich Syndrome, Glanzmann Thrombasthenia, or Chediak-Higashi Syndrome. Investigators should contact the PI if a patient has a history of severe thrombocytopenia due to a cause not listed here or if any other clarification is needed.
11. Known immediate or delayed hypersensitivity reaction or idiosyncrasy to drugs chemically related to bomedemstat or LSD1 inhibitors (i.e., monoamine oxidase inhibitors; MAOIs) that contraindicates their participation.
12. Any hypersensitivity to PD-1/PD-L1 targeting agents.
13. Current use of monoamine oxidase A and B inhibitors (MAOIs).
14. Current use of a prohibited medication (e.g. romiplostim) or expected to require any of these medications during treatment with the investigational drug.
15. Current or anticipated use of an antiplatelet (e.g. clopidogrel), anticoagulant (e.g. warfarin or apixaban), or NSAID with antiplatelet activity (e.g. aspirin, ibuprofen), that, in the opinion of the investigator, could NOT be safely discontinued when the subject's platelet count decreases below $50 \times 10^3/\text{mcL}$.
16. Has undergone major surgery within 4 weeks prior to starting study drug and/or has not recovered from side effects of such surgery. **Note:** Major surgery and recovery are defined at the discretion of the investigator.
17. Receipt of a live vaccine within 30 days of first dose of study therapy.
18. Uncontrolled active infection.

19. Any concomitant active malignancy considered clinically significant by the investigator.
20. Known human immunodeficiency virus (HIV) infection or known active Hepatitis B or Hepatitis C virus infection (testing will not be conducted as part of Screening procedures).
21. History of any illness/impairment of gastrointestinal (GI) function that might interfere with drug absorption (e.g. chronic diarrhea), confound the study results or pose an additional risk to the patient by participation in the study.
22. Use of an investigational agent within 28 days, or the equivalent of at least 7 half-lives of that agent, whichever is the shorter, prior to the study Day 1.
23. Females who are pregnant or breastfeeding or plan to become pregnant or breastfeed at any time during the study.

6.0 TREATMENT PLAN

6.1 Study Overview

This is an open label, single arm, single institution Phase 1-2 study testing the activity and tolerability of the LSD1 inhibitor bomedemstat in combination with maintenance immune checkpoint inhibitor (ICI) in patients with newly diagnosed extensive stage SCLC treated with first-line induction platinum-etoposide and ICI. Bomedemstat dosing will be titrated to platelet count suppression (an on-target toxicity). Consideration of bomedemstat dose escalation will occur on an every three week schedule. As such, for convenience, all patients will receive the ICI atezolizumab in combination with bomedemstat, including patients who received a different ICI as part of induction with platinum-etoposide.

The starting dose of bomedemstat will be determined according to the screening platelet count as follows. For patients with a platelet count of $\geq 100 \times 10^3/\text{mCL}$, the starting dose will be 0.5 mg/kg/d. For patients with a platelet count of $75-99 \times 10^3/\text{mCL}$, the starting dose will be 0.4 mg/kg/d. See Sections 2.7 and 3.1.4 for bomedemstat starting dose selection rationale. A safety evaluation will be performed as described in Section 10.2 and the starting dose will be modified accordingly, if necessary.

Bomedemstat will be administered orally, once daily, for a 21-day cycle. Bomedemstat should be taken on an empty stomach. See Section 3.1.5 for detailed administration instructions. Because bomedemstat exhibits on-target toxicity of lineage-specific myelosuppression that preferentially affects platelet production, bomedemstat dosing will be titrated to a target platelet count of $50-99 \times 10^3/\text{mCL}$ as described in Section 6.2. Detailed guidance regarding bomedemstat dose modification for toxicities (including myelosuppression) is described in Section 6.3.

Atezolizumab will be administered via IV infusion at a flat dose of 1,200 mg every 3 weeks in keeping with the medication's prescribing information regarding standard of care use⁴⁶.

Subjects who at any time experience severe toxicity meeting criteria for treatment discontinuation (see Section 6.6.2) will not be eligible for further study treatment and will be converted to Off Treatment status.

Radiographic disease response assessments will occur every 6 weeks +/- 7 days (after completion of 24 weeks of study treatment, the interval can be extended to every 9 weeks +/- 7 days at the discretion of the investigator) for the duration of study participation with disposition based on the results as follows:

1. Subjects who experience disease response (CR or PR) or stable disease without evidence of clinical deterioration will continue bomedemstat and atezolizumab maintenance therapy. Absence of clinical deterioration is determined by the treating physician and is defined as follows:

- a. Absence of signs and symptoms of disease progression.
- b. Absence of rapid disease progression.
- c. Absence of progressive tumor at critical anatomical sites (e.g. cord compression) requiring urgent alternative medical intervention.

2. Subjects who experience disease progression that is isolated to the CNS are eligible to continue study treatment following definitive therapy to the CNS disease, provided that ongoing study treatment is likely to provide additional benefit to the patient, at the discretion of the investigator and after appropriate discussion with the patient. See Section 8.2.7.1 for further details.
3. Subjects who experience confirmed disease progression by RECIST 1.1 (other than isolated CNS progression) and/or clinical deterioration should discontinue study treatment (see Section 6.6.1).

Note: Subjects with unconfirmed disease progression by RECIST 1.1 who do not have evidence of clinical deterioration may continue to receive study treatment, at the discretion of the investigator and after appropriate discussion with the patient. Subjects should be monitored closely and a follow-up scan should be performed after 28 days, or sooner if clinical deterioration occurs. If the follow-up scan confirms disease progression, the subject should discontinue study treatment. See Section 8.2.7.2 for further details.

Subjects will be followed closely until disease progression per RECIST 1.1 or initiation of new anticancer treatment, whichever occurs first; and will afterwards be followed for survival until death or study termination, whichever occurs first. Blood samples for biomarker assessments will be collected at protocol-defined timepoints to support study endpoints.

